Study Protocol

Protocol Title: Cranial electric stimulation (CES) to modify suicide risk factors in psychiatric inpatients

Study No.: HP-00065640, Date 6th February 2016

Principal Investigator: [name] MD, [contact], [contact] (24 hour access)

Brief Summary

This pilot study aims to investigate whether a treatment called cranial electric stimulation or CES can decrease risk factors for suicide. The specific CES device we will use is called Alpha-Stim®. CES will be used in addition to usual treatment (medication and group therapy).

Detailed Description

Suicide is still a major issue in the United States and all around the world. There are many reasons for people attempting suicide and the major modifiable risk factors are depression, anxiety, insomnia, and agitation. The standard treatment for all suicidal patients includes medication, admission to a hospital and reducing the risk factors. Medications have potential side effects and concerns about the drug interactions. One of the biological treatment alternatives to medication is cranial electric stimulation. This technique uses a device to stimulate the brain through electrical current. Using an Alpha-Stim® device, current is applied to the brain using skin electrodes which can be easily clipped on to the earlobe. The amount of current used is very low and is 1/1000th of the current used for electroconvulsive therapy (ECT) and 1/10th to 1/20th of the 1-2 milli amperes used with transcranial direct current stimulation (tDCS). Our goal is to examine the safety and efficacy of this device when used as an add-on or adjunctive treatment to the usual treatments during the inpatient stay.

Study Type: Interventional

Study Phase: 4

Study Design

Allocation: Randomized Intervention Model: Parallel Assignment

Masking: Double Blind (Participant, Care Provider, Investigator, Outcomes Assessor)

Primary Purpose: Treatment

Conditions:

- Suicide
- Depression

- Anxiety
- Insomnia
- Agitation

Intervention Device: Alpha-Stim®. Study Arms • Experimental: Adjunctive CES

CES 100µA for one hour daily, five to seven days per week. Rating scales will be administered at baseline (i.e., pre-treatment), twice a week and at the end of the study.

Intervention: Device: Alpha-Stim®.

Sham Comparator: Sham control CES

For the sham group the Alpha-Stim® will not emit electricity. All other procedures will be the same for both the sham group and the active CES group. The current intensity will be preset and locked by the manufacturer. The sham devices will appear identical to the active device.

Intervention: Device: Alpha-Stim

Primary Outcome Measures:

Change in the modifiable suicide risk factors (MSRF's)

To assess the efficacy of adjunctive cranial electric stimulation (CES), specifically Alpha-Stim®, to reduce suicide risk in psychiatric inpatients through a randomized, double-blind, sham-controlled, clinical trial. The primary efficacy outcome measure will be change in the modifiable suicide risk factors (MSRF's) as indicated by a summed global score from rating scales measuring the MSRFs that include depression (Montgomery-Åsberg Depression Rating Scale), anxiety (Hamilton Anxiety Rating Scale), insomnia (The Pittsburgh Sleep Quality Index) and agitation (Agitated Behavior Scale).

Assess adverse effects and safety

To assess safety of adjunctive cranial electric stimulation (CES), specifically Alpha-Stim®, to reduce suicide risk in psychiatric inpatients through a randomized, double-blind, sham-controlled, clinical trial. The primary safety outcome measure will be responses to an adverse effect assessment questionnaire (GASE questionnaire).

Secondary Outcome Measures:

Assess length of stay

## **Method**

Analysis done in R Version 3.4.1

### **Random forest results:**

[figure not shown]
All random forest models were run to create 2001 trees.

*Random forest model predicting treatment group (Active vs Sham)*

[figure not shown]
OOB (out-of-bag) error rate: 60%

- This means that the model was wrong 60% of the time and correct 40% of the time.

Here is a plot showing how the model is converging as the number of trees increases. Overall this is the inverse of what you would want to see. Optimally you want the error to start high and decrease to a convergence or a plateau as the number of trees increases. The convergence is settling at an error of  $\sim 0.6$ , which is your OOB error rate.

[figure not shown]

For reference this is what a more favorable plot looks like. This plot has an OOB error rate of 5.73%.

Back to your data, here are the experimental variables that are most predictive of treatment group. There are 2 accuracy metrics here that are used interchangeably based on the preference of the investigator. The accuracy numbers are a bit arbitrary and there is no threshold of significance per se. These are simply the most predictive variables of the target experimental variable.

rf

[figure not shown]
*Random forest model predicting Montgomery-Asberg Depression Scale change between the final observation and baseline (MADRA\_Delta)*

The MADRA\_Delta score is continuous; therefore, the model produces a % variation explained rather than an OOB error rate.

[figure not shown]
% variation explained: 14.14%

- Meaning that ~85% of the variation is unexplained

Here is the plot showing how the model is converging. Again the model is not converging very well.

Here are the experimental variables that are explaining the most variation or are the most predictive of the MADRA\_Delta score. It is encouraging that HAMAT\_Delta score and PSQI-Delta score are two of the best predictors of MADRA\_Delta score.

[figure not shown]

*Random forest model predicting Hamilton Depression Score change between the final observation and baseline (HAMAT\_Delta)*

% variation explained: 0.83%

[figure not shown]
- Meaning that ~99% of the variation is unexplained

Here is the plot showing how the model is converging. Again the model is not converging very well.

Here are the experimental variables that are explaining the most variation or are the most predictive of the HAMAT\_Delta score. It is encouraging that MADRA\_Delta score is one of the best predictors of HAMAT\_Delta score.

rf

[figure not shown]

Random forest model predicting Pittsburg Sleep Quality Index score change between the final observation and baseline (PSQI\_Delta).

% variation explained: 13.01%

[figure not shown]
- Meaning that ~87% of the variation is unexplained

Here is the plot showing how the model is converging. Better.

Here are the experimental variables that are explaining the most variation or are the most predictive of the PSQI\_Delta score. It is encouraging that MADRA\_Delta score is one of the best predictors of PSQI\_Delta score.

rf

[figure not shown]
Random forest model predicting Length of Stay (LOS).

% variation explained: 18.7%

- Meaning that ~81% of the variation is unexplained

[figure not shown]
Here is the plot showing how the model is converging.

[figure not shown]
Here are the experimental variables that are explaining the most variation or are the most predictive of the LOS.

rf

[figure not shown]

[figure not shown]
[figure not shown]
I made some box plots of the target variables with notches. If the notches are overlapping that means that the difference is not significant.

MADRA\_Delta

HAMAT\_Delta

I also ran some linear models on the target variables to see if there was a significant proportion of the variation explained by the treatment. Here are the various models. A summary of the results is that none of the target variables explained a significant proportion of the variance in the treatment variable. In addition the treatment variable did not explain a significant proportion of the variance in any of the target variables.

Active vs Sham

```
Call:
lm(formula = dat$Active_vs._Sham ~ dat$MADRA_Delta + dat$PSQI_Delta +
    dat$LOS + dat$HAMAT_Delta)

Residuals:
    Min       1Q   Median       3Q      Max
-0.7116 -0.4783  0.1233  0.4296  0.6952

Coefficients:
                Estimate Std. Error t value Pr(>|t|)
(Intercept)    1.680905   0.272114   6.177 1.85e-06 ***
dat$MADRA_Delta -0.008970   0.014086  -0.637   0.530
dat$PSQI_Delta  0.024970   0.021857   1.142   0.264
dat$LOS        -0.014567   0.011225  -1.298   0.206
dat$HAMAT_Delta 0.006887   0.019592   0.352   0.728
---
Signif. codes:  0 '***' 0.001 '**' 0.01 '*' 0.05 '.' 0.1 ' ' 1

Residual standard error: 0.5104 on 25 degrees of freedom
Multiple R-squared:  0.1317,    Adjusted R-squared:  -0.007216
F-statistic: 0.9481 on 4 and 25 DF,  p-value: 0.4529
```

MADRA\_Delta

```

Call:
lm(formula = dat$MADRA_Delta ~ dat$HAMAT_Delta + dat$PSQI_Delta +
    dat$Active_vs._Sham + dat$LOS)

Residuals:
    Min       1Q   Median       3Q      Max
-19.1440  -4.4362   0.3207   4.8098  13.4379

Coefficients:
                Estimate Std. Error t value Pr(>|t|)
(Intercept)    -4.75714    4.17875  -1.138  0.265741
dat$HAMAT_Delta  0.84571    0.21889   3.864  0.000703 ***
dat$PSQI_Delta  0.65285    0.28752   2.271  0.032044 *
dat$Active_vs._Sham1 -1.77929    2.79430  -0.637  0.530071
dat$LOS         -0.07574    0.16263  -0.466  0.645431
---
Signif. codes:  0 '***' 0.001 '**' 0.01 '*' 0.05 '.' 0.1 ' ' 1

Residual standard error: 7.188 on 25 degrees of freedom
Multiple R-squared:  0.5498,    Adjusted R-squared:  0.4778
F-statistic: 7.633 on 4 and 25 DF,  p-value: 0.0003661

```

HAMAT\_Delta

```

Call:
lm(formula = dat$HAMAT_Delta ~ dat$MADRA_Delta + dat$PSQI_Delta +
    dat$Active_vs._Sham + dat$LOS)

Residuals:
    Min       1Q   Median       3Q      Max
-10.2459  -2.5605   0.1305   1.8374  11.9851

Coefficients:
              Estimate Std. Error t value Pr(>|t|)
(Intercept)   -5.84565    2.86952  -2.037 0.052353 .
dat$MADRA_Delta  0.44207    0.11442   3.864 0.000703 ***
dat$PSQI_Delta  -0.05453    0.22805  -0.239 0.812978
dat$Active_vs._Sham1 0.71411    2.03158   0.352 0.728154
dat$LOS         0.26534    0.10549   2.515 0.018688 *
---
Signif. codes:  0 '***' 0.001 '**' 0.01 '*' 0.05 '.' 0.1 ' ' 1

Residual standard error: 5.197 on 25 degrees of freedom
Multiple R-squared:  0.5646,    Adjusted R-squared:  0.4949
F-statistic: 8.104 on 4 and 25 DF, p-value: 0.000247

```

PSQI\_Delta

```

Call:
lm(formula = dat$PSQI_Delta ~ dat$MADRA_Delta + dat$HAMAT_Delta +
    dat$Active_vs._Sham + dat$LOS)

Residuals:
    Min       1Q   Median       3Q      Max
-11.3494  -2.1282   0.1626   1.9709   9.8305

Coefficients:
              Estimate Std. Error t value Pr(>|t|)
(Intercept)    0.65390    2.71122    0.241  0.811
dat$MADRA_Delta  0.26188    0.11534    2.271  0.032 *
dat$HAMAT_Delta -0.04184    0.17500   -0.239  0.813
dat$Active_vs._Sham1 1.98695    1.73926    1.142  0.264
dat$LOS        -0.04182    0.10311   -0.406  0.688
---
Signif. codes:  0 '***' 0.001 '**' 0.01 '*' 0.05 '.' 0.1 ' ' 1

Residual standard error: 4.553 on 25 degrees of freedom
Multiple R-squared:  0.2684,    Adjusted R-squared:  0.1513
F-statistic: 2.293 on 4 and 25 DF,  p-value: 0.08759

```

LOS

```

Call:
lm(formula = dat$LOS ~ dat$MADRA_Delta + dat$PSQI_Delta + dat$Active_vs._Sham +
    dat$HAMAT_Delta)

Residuals:
    Min       1Q   Median       3Q      Max
-12.844  -4.353  -2.341   2.845  23.249

Coefficients:
              Estimate Std. Error t value Pr(>|t|)
(Intercept)    20.0404    3.3876   5.916 3.57e-06 ***
dat$MADRA_Delta  -0.1136    0.2438   -0.466  0.6454
dat$PSQI_Delta  -0.1563    0.3854   -0.406  0.6885
dat$Active_vs._Sham1 -4.3329    3.3387   -1.298  0.2062
dat$HAMAT_Delta  0.7611    0.3026    2.515  0.0187 *
---
Signif. codes:  0 '***' 0.001 '**' 0.01 '*' 0.05 '.' 0.1 ' ' 1

Residual standard error: 8.802 on 25 degrees of freedom
Multiple R-squared:  0.3168,    Adjusted R-squared:  0.2075
F-statistic: 2.898 on 4 and 25 DF,  p-value: 0.04239

```

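### The forest ranking for treatment arm cannot be told from noise, and the outcome-change rankings show only that concurrent scales move together

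*SAP*

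**What the plan says.** The section of the SAP on random forest results reports one forest for treatment arm and one each for MADRS change, HAMAT change, PSQI change and length of stay.

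- **Arm.** The SAP interprets the out-of-bag (OOB) result itself: "This means that the model was wrong 60% of the time and correct 40% of the time". It then introduces a ranking with the words "here are the experimental variables that are most predictive of treatment group", and adds the caveat "The accuracy numbers are a bit arbitrary and there is no threshold of significance per se".
- **MADRS change.** "variation explained: 14.14" per cent. HAMAT change and PSQI change "score are two of the best predictors of" the MADRS change score, which the SAP finds encouraging.
- **HAMAT change.** "variation explained: 0.83" per cent, with MADRS change named among the best predictors and the same favourable remark.
- **PSQI change.** 13.01% explained, again with MADRS change named and welcomed.
- **Length of stay.** 18.7% explained; the text names no predictor.

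The SAP heading calls HAMAT a Hamilton depression score, while the protocol's primary outcome lists the Hamilton Anxiety Rating Scale. It is read here as HAM-A; the label should be reconciled.

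**The concern.** An importance ranking always has a top, whether or not the forest predicts anything. A list drawn from a forest that does no better than guessing gives the reader variable names without evidence behind them.

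The three symptom forests raise a separate question. A change score measured over the same weeks as the target is not a predictor in the sense a trial reader expects. It is neither known at baseline nor assigned by the trial. If such scores are inputs, a high rank says that two scales improved together. It does not say that treatment worked, or which patients respond.

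At stake is how the forest output is read. The protocol asks whether active stimulation changes the risk factors compared with sham, and these lists do not bear on that.

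**Working it through.** **What can be reproduced.** The forests cannot be rerun: data, predictor list and tuning settings are not given. The printed linear models can be checked. For the arm model, R² = 0.1317 with 4 and 25 degrees of freedom:

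- F = (0.1317/4) / (0.8683/25) = 0.948 (printed 0.9481), p = 0.4529 (as printed).
- Adjusted R² = 1 − 0.8683 × 29/25 = −0.007 (as printed).

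The other four models also reproduce to rounding.

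**Arm sizes.** 25 residual degrees of freedom + 5 coefficients = 30 patients. The total sum of squares for arm is 0.5104² × 25 / 0.8683 = 7.50. With arm codes one unit apart this equals n₁n₂/30, which is 7.50 for 15:15 and 7.47 for 14:16. The split is therefore 15:15, and guessing is wrong 50% of the time.

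**Is 60% error distinguishable from guessing?** Assume the forest used the same 30 patients, so 18 were wrong and 12 correct.

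- P(12 or fewer correct of 30, at 0.5) = 0.18.
- Exact 95% interval for the error rate: 41% to 77%.
- OOB votes are not independent, so null forests were also simulated. The numbers of noise predictors are assumptions. With 10 noise predictors (301 trees, 150 runs) the mean OOB error was 54%, and 35% of runs reached 60% or more. With 5, 15 or 40 noise predictors added to four variables unrelated to arm (200 trees, 40 runs each), the means were 55% to 57%, and 38% to 45% of runs reached 60% or more.
- The arm linear model agrees: R² of 0.132 is below the 4/29 = 0.138 expected from four unrelated predictors.

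**What drives the symptom lists?** Each printed t value gives a partial correlation, t/√(t² + 25). For MADRS with HAM-A, 3.864/√(3.864² + 25) = 0.61. For MADRS with PSQI, 2.271/√(2.271² + 25) = 0.41. Inverting the matrix of all ten gives the simple correlations. As a check, it returns the five printed R² values (0.132, 0.550, 0.565, 0.268, 0.317).

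| Pair | Simple r |
|---|---|
| MADRS change, HAM-A change | 0.668 |
| MADRS change, PSQI change | 0.452 |
| Arm, MADRS change | −0.068 |
| Arm, HAM-A change | −0.102 |
| Arm, PSQI change | 0.199 |

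Removing arm:

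- MADRS with HAM-A: (0.668 − 0.068 × 0.102) / √[(1 − 0.068²)(1 − 0.102²)] = 0.661/0.992 = 0.67.
- MADRS with PSQI: (0.452 + 0.068 × 0.199) / √[(1 − 0.068²)(1 − 0.199²)] = 0.466/0.978 = 0.48.

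The scales move together within arm, so co-outcomes can head these lists with no treatment effect at all. In simulated HAM-A forests with this correlation structure (same assumed settings as the second simulation above), MADRS change ranked in the top three in 95% to 100% of runs. OOB variation explained was 0.83% or less in 7% to 20% of runs, so a real correlate can sit in a forest with almost no measured skill.

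**One association, shown twice.** t = 3.864 appears in both the MADRS and HAM-A linear models, and t = 2.271 in both the MADRS and PSQI models. That each scale ranks highly for the other is not mutual confirmation.

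**The case against.** The SAP is open about much of this. It says the arm model is mostly wrong, that its convergence plot runs the opposite way to what one would want, that the MADRS and HAM-A forests converge poorly, and that "there is no threshold of significance per se" for the importance numbers. Its linear-model summary reports no significant share of variance explained by treatment. It never claims that the rankings show efficacy or identify responders. Finding it encouraging that the scales agree could even be relevant, since the protocol sums them into one score. All of this stands, and it limits the weight of the point. It does not rescue the arm list, which is still presented as the most predictive variables.

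Four stronger readings are tempting, and the documents do not support them.

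- *All the forests lack skill.* The MADRS, PSQI and length-of-stay forests report 14.14%, 13.01% and 18.7% explained.
- *The HAM-A list is noise, because 0.83% is explained.* The one predictor the text names for it has p = 0.000703 in the linear model. The association is real; it is concurrent.
- *Other outcomes fed every forest.* The text shows this for the MADRS, HAM-A and PSQI forests only. The importance plots are not visible, and inputs to the arm and length-of-stay forests are not stated.
- *60% error means the arm forest is worse than chance.* At P = 0.18, and with null forests averaging 54% to 57%, it is an ordinary result with no signal.

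**Conclusion.** The concern holds in two separate parts. The arm ranking comes from a forest indistinguishable from guessing and should not be shown. The MADRS, HAM-A and PSQI rankings are circular: they restate real correlations between concurrent outcomes, so 14.14%, 0.83% and 13.01% say nothing about prediction from arm or baseline.

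The severity is minor, because no efficacy claim rests on the forests and the conclusion on treatment does not change. The 0.18 assumes that the forest used the 30 patients of the linear models, a number the forest text does not state. The simulations are illustrative, with assumed predictor counts and fewer trees than the SAP's 2001. The correlations follow from printed output alone.

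**What to change.** 1. Remove the ranking from the arm forest. Report only its OOB error, with a permutation p-value from re-shuffled arm labels.
2. Rerun the MADRS, HAM-A and PSQI forests with arm and baseline variables only, excluding post-baseline outcomes wherever they were inputs. Alternatively, keep the present lists but describe them as correlations between concurrent outcomes, and delete the remarks that treat them as encouraging evidence of prediction.
3. Where the rerun OOB skill does not exceed its permutation null, state that no predictor was identified.
4. Label the forests exploratory. Take the treatment effect from a model of each outcome on arm, with that outcome's baseline value and without the other outcomes as covariates. No such model is printed; every printed outcome model adjusts for the other outcomes.

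The cost is re-running existing data and changing some wording. The downside is small: most of the ranked lists will probably disappear, and the percentages explained will probably fall.

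### The SAP treats two forest importance metrics as interchangeable by preference; if they are the usual R pair they can rank differently, which exposes the treatment-group list and the lower-ranked entries.

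*SAP*

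**What the plan says.** The SAP's Random forest results section fits five forests: one for treatment group and one each for the changes in MADRS, HAM-A and PSQI and for length of stay. "All random forest models were run to create 2001 trees", and under Method, "Analysis done in R Version 3.4.1".

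The rule for reading variable importance is given once, under the treatment-group forest: "There are 2 accuracy metrics here that are used interchangeably based on the preference of the investigator". The next two sentences are "The accuracy numbers are a bit arbitrary and there is no threshold of significance per se" and "These are simply the most predictive variables of the target experimental variable".

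That forest is reported with "OOB (out-of-bag) error rate: 60" per cent. The outcome forests explain 14.14% (MADRS), 0.83% (HAM-A), 13.01% (PSQI) and 18.7% (length of stay) of the variation. A list of top variables follows each forest, and three of the four outcome lists draw a favourable comment, for example "It is encouraging that HAMAT\_Delta score and PSQI-Delta score are two of the best predictors of MADRA\_Delta score". No predictor is named in the text for length of stay.

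The readable text gives neither the names of the metrics nor the list of candidate predictors. The figures are not shown and some SAP passages were not available, so this is a limit of the review and not a fault of the plan.

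**The concern.** A list of the most predictive variables has meaning only if the rule that orders it is fixed. Here the rule is left to preference between two metrics, with no reference level for what noise would produce.

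If the pair is the standard one, the metrics measure different things. Permutation importance is computed on out-of-bag patients and is centred near zero for a noise variable. Impurity importance is computed in the training sample, is never negative, and grows with the number of available split points. A two-level variable, such as treatment, is therefore placed below change scores and length of stay even when none of them is associated with the target.

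At stake is which variables are reported as predictive, and so which might be taken forward as hypotheses. The trial's treatment conclusion is not at stake.

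**Working it through.** **Inputs.** 2001 trees (SAP, Random forest results). Sample size from the linear models in the same section: "Residual standard error: 0.5104 on 25 degrees of freedom", and 25 + 5 coefficients = 30. That the forests used the same 30 patients is an assumption. So is the metric pair, which is inferred from the R output style: out-of-bag error for the categorical target, per cent variation explained for continuous targets, and two metrics per list.

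**Reproducing the plan's own figures.** No forest output can be reproduced without patient data. The linear models can be checked with F = (R²/4)/((1 − R²)/25):
- Treatment: (0.1317/4)/(0.8683/25) = 0.948, p = 0.453 (printed 0.9481, 0.4529).
- MADRS change: (0.5498/4)/(0.4502/25) = 7.63, p = 0.00037 (printed 7.633, 0.0003661).
- The other three models also agree, which confirms n = 30 there.

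**The treatment forest.** 60% of 30 is 18 errors. Under coin-tossing, P(18 or more of 30) = 0.181. In the simulated noise classification forests below, mean out-of-bag error was 53% to 54%, and 33% to 38% of runs reached 60% or more. The stated 60% is what noise would give.

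**Do the metrics agree in noise?** R randomForest, n = 30, 2001 trees, default settings, 500 runs per scenario. All predictors are unrelated to the target. The mixed list is assumed: two binary, one 3-level, one 5-level and four continuous variables.

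| Scenario | Continuous variable first: impurity / permutation (fair) | Same top variable | Same top-three set |
|---|---|---|---|
| Mixed list, classification | 98.4% / 58.8% (50%) | 51% | 7.6% |
| Mixed list, regression | 98.4% / 52.4% (50%) | 38.8% | 6.2% |
| Treatment + three continuous, regression | 100% / 79.8% (75%) | 54.2% | 24.8% |
| Four continuous, classification | not applicable | 79.2% | 70.0% |

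In the third row, impurity ranked treatment last in 100% of runs and permutation in 24.8% (fair value 25%). This bears on the trial only if treatment was a predictor in the outcome forests, which the readable text does not say. In the fourth row no type bias is possible, yet the top variable still differs in 100 − 79.2 = 20.8% of runs.

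A different assumed mix (10 continuous, 10 binary, 300 runs) gave the same pattern. The impurity top five held 4.9 continuous variables against 3.0 for permutation, and the two top-five lists shared 2.9 (classification) and 2.6 (regression) variables.

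**Do the named predictors depend on the metric?** The five printed regressions determine the sample correlations. With residual variance s² for each target, the inverse covariance matrix has diagonal 1/s² and off-diagonal −b/s². Inverting it gives `MADRA_Delta` with `HAMAT_Delta` 0.67 and `MADRA_Delta` with `PSQI_Delta` 0.45. Forests simulated with these correlations (normal data, 10 continuous and 10 binary predictors filled up with noise, 200 runs per target) gave:
- MADRS forest: same top variable in 97% of runs. `HAMAT_Delta` was in the top five in 100% under both metrics; `PSQI_Delta` in 97.5% (permutation) and 100% (impurity).
- HAM-A forest: same top variable in 96.5%. `MADRA_Delta` was in the top five in 100% under both.
- PSQI forest: same top variable in 74%. `MADRA_Delta` was in the top five in 98.5% and 100%.
- The two top-five lists still shared only 2.9 to 3.4 of five variables.

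So the named predictors hold under either metric, while the lower positions do not. One limit is that the mean simulated fit (20%, 20%, −6%) does not match the stated 14.14%, 0.83% and 13.01%.

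**The case against.** The strongest reply is that the premise cannot be seen. The metrics, the package and the predictor list are not in the readable text, and the only two-level variable visible is treatment. This stands as a limit on size. If all predictors are many-valued, the type bias disappears and only the smaller disagreement in the fourth row remains.

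A reader might infer that the predictors named in the text are artefacts of the metric. The documents do not support that. The linear models have no split-point bias, and they give t = 3.864, p = 0.0007 for the HAM-A and MADRS changes and t = 2.271, p = 0.032 for the PSQI and MADRS changes. The noise agreement rates do not describe those pairs.

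A reader might also infer that the investigator saw both rankings and picked one. Nothing shows this: the sentence may simply describe common practice, and both metrics may have been plotted. What stands is that the SAP adopts the practice and, in the readable text, fixes no metric.

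It is also fair to say that the SAP is candid. It calls the numbers somewhat arbitrary, reports how much variation is unexplained, and says that convergence is poor for several forests. That candour does not fit with reading the lists at face value.

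Finally, a shuffled-target null would calibrate impurity importance too, so permutation importance is not the only defensible choice. This is correct. The case for permutation is that it is the one of the pair that measures out-of-bag accuracy.

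**Conclusion.** The point holds as a minor one. The rule that the two metrics may be swapped by preference is wrong if they are permutation and impurity importance. At this sample size and tree count, noise alone makes them disagree on the top variable in about 21% of runs with only many-valued predictors, and in about 49% to 61% with the assumed mixed list.

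The affected results are the treatment-group list, whose forest predicts no better than chance, and the unnamed lower-ranked entries in the other lists. The effect on this trial's own lists cannot be sized without the predictor list and the data.

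It does not follow that the null treatment result is in doubt. That conclusion comes from the linear models, which use no importance metric.

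**What to change.** 1. Delete the sentence that makes the two metrics interchangeable, and state out-of-bag permutation importance as the metric for every list. Impurity importance may be shown as supplementary.
2. For each forest, refit with the target shuffled (for example 500 times) and record the largest importance across predictors each time. Call a variable predictive only if it exceeds the 95th percentile of that maximum. A per-variable 95th percentile is too loose: with 20 noise predictors it would name 20 × 0.05 = 1 per forest, or about 5 over five forests.
3. Replace the statement that there is no threshold with this one.
4. Do not interpret the importance list from the treatment-group forest.

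The cost is a few minutes of computing and a few changed sentences. Some variables now listed may drop out.

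### The printed linear models adjust each arm comparison for the other outcomes, so their arm coefficients do not estimate the randomised treatment effect on each outcome

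*SAP*

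**What the plan says.** The symptom outcomes are changes from baseline to the final observation. The SAP (Random forest results) introduces them as "Random forest model predicting Montgomery-Asberg Depression Scale change between the final observation and baseline" (MADRA_Delta), "Random forest model predicting Hamilton Depression Score change between the final observation and baseline" (HAMAT_Delta) and "Random forest model predicting Pittsburg Sleep Quality Index score change between the final observation and baseline" (PSQI_Delta). HAMAT is read here as the protocol's Hamilton Anxiety scale; the depression label is a separate matter.

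After the forests, the SAP gives linear models run "to see if there was a significant proportion of the variation explained by the treatment". The covariates are:

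- MADRA_Delta: begins "lm(formula = dat$MADRA_Delta ~ dat$HAMAT_Delta + dat$PSQI_Delta" and continues with arm and LOS.
- HAMAT_Delta: begins "lm(formula = dat$HAMAT_Delta ~ dat$MADRA_Delta + dat$PSQI_Delta" and continues with arm and LOS.
- PSQI_Delta: the other two change scores, arm and LOS.
- LOS: the three change scores and arm.
- A fifth model takes arm as the response and the four outcomes as predictors.

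Part of the SAP's summary of these models is that "the treatment variable did not explain a significant proportion of the variance in any of the target variables". The SAP also says "I made some box plots of the target variables with notches"; those figures are not shown in the text available for this review.

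The protocol (Primary Outcome Measures) takes as its efficacy outcome the change in a score summed over depression, anxiety, insomnia and agitation. It lists length of stay under Secondary Outcome Measures.

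**The concern.** Randomisation makes the arms comparable on everything fixed at baseline. It does not make them comparable among patients who had the same change on two other scales and the same stay. Those quantities are outcomes that treatment may itself affect. An arm coefficient that holds them fixed answers a different question from whether assignment to active stimulation changed this outcome.

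This matters for the protocol's hypothesis, which is joint improvement across several risk factors. If treatment moved the scales together, holding the others fixed could remove part of the shared improvement from each coefficient. A pilot is read mainly for its estimates and intervals, and the per-outcome estimates printed here are conditional ones.

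**Working it through.** **Inputs.** Coefficients, residual standard errors s and R² from the five printed regressions, each on 25 residual df. With 5 parameters, n = 25 + 5 = 30.

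**1. Reproduce the printed arm tests (t = estimate / SE, 25 df).**
- HAMAT_Delta: 0.71411 / 2.03158 = 0.352, p = 0.728
- MADRA_Delta: -1.77929 / 2.79430 = -0.637, p = 0.530
- PSQI_Delta: 1.98695 / 1.73926 = 1.142, p = 0.264
- LOS: -4.3329 / 3.3387 = -1.298, p = 0.206

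All agree with the SAP.

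**2. Arm sizes.** Total sum of squares = 25s²/(1 - R²). For the arm-as-response model this is 25 × 0.5104² / 0.8683 = 7.50. With two arms it equals n1·n2/30, so n1·n2 = 225 and there are 15 per arm.

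**3. Arm-alone differences.** For least squares, the arm coefficient with covariates equals the arm-alone difference d for that outcome minus the sum of (printed slope × arm-alone difference of each covariate). The four models give four equations in four unknowns. The solution is M = -1.333 (MADRA_Delta), H = -1.466 (HAMAT_Delta), P = +1.933 (PSQI_Delta), L = -5.599 (LOS). Substituting back:
- H: -1.466 - 0.44207(-1.333) + 0.05453(1.933) - 0.26534(-5.599) = +0.714
- M: -1.333 - 0.84571(-1.466) - 0.65285(1.933) + 0.07574(-5.599) = -1.779
- P: 1.933 - 0.26188(-1.333) + 0.04184(-1.466) + 0.04182(-5.599) = +1.987
- L: -5.599 + 0.1136(-1.333) + 0.1563(1.933) - 0.7611(-1.466) = -4.333 (to rounding)

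Each returns the printed coefficient. Rounding in the printed output moves the solved differences by no more than about 0.002.

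**4. Standard errors.** Residual sum of squares with arm alone = 25s²/(1 - R²) - 7.5d², on 28 df; SE = within-arm SD × √(2/15). For MADRA_Delta: 25 × 7.188² / 0.4502 = 2869.1; minus 7.5 × 1.333² = 13.3 gives 2855.8; SD = √(2855.8/28) = 10.10; SE = 3.69. With t = 2.048, the half-width is 7.55. The other outcomes follow the same way.

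| Outcome | Arm alone (SE) | 95% CI | p | As printed (SE) | 95% CI |
|---|---|---|---|---|---|
| HAMAT_Delta | -1.47 (2.70) | -7.00 to 4.07 | 0.59 | +0.71 (2.03) | -3.47 to 4.90 |
| MADRA_Delta | -1.33 (3.69) | -8.89 to 6.22 | 0.72 | -1.78 (2.79) | -7.53 to 3.98 |
| PSQI_Delta | +1.93 (1.80) | -1.75 to 5.62 | 0.29 | +1.99 (1.74) | -1.60 to 5.57 |
| LOS | -5.60 (3.52) | -12.81 to 1.61 | 0.12 | -4.33 (3.34) | -11.21 to 2.54 |

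Adjusting for LOS alone already takes HAMAT_Delta to +0.62, so LOS accounts for most of that shift. A simulated 95% interval for the whole HAMAT_Delta shift (+2.18) is -2.1 to 6.8, so the sign change is within sampling error.

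**5. What the arm-as-response model tests.** With two groups, its overall F is Hotelling's test of arm on the four outcomes together. T² = 28 × 0.1317 / 0.8683 = 4.25, and F = 4.25 × 25 / (4 × 28) = 0.948 on 4 and 25 df, p = 0.453, as printed.

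**The case against.** **A valid arm comparison is already printed.** The overall F of the arm-as-response model (p = 0.453) holds no post-randomisation outcome fixed, and it supports the SAP's null message for the four outcomes jointly. This stands. It gives no estimate or interval for any single outcome, and it does not test the protocol's summed score, since agitation is in none of the printed models.

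**The box plots may be unadjusted.** They may be, but the text gives no estimate or interval from them.

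**The loss from conditioning is uncertain.** This stands too. Suppose treatment gave an equal benefit in SD units on the three scales and left LOS unchanged. The printed slopes would then keep 6% of the effect for MADRS, 43% for HAM-A and 53% for PSQI. With 30 patients the simulated 95% ranges are about -18% to 35%, 19% to 75% and 19% to 95%. If LOS also moved by one SD, HAM-A would keep about 9% or 78%, depending on direction. In the actual data the printed MADRS coefficient is further from zero than the arm-alone one. Understatement is therefore a possibility, not a general rule.

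**Stronger readings to avoid.**
- A reader might infer from the undated final observation that the arms were rated at different times, or that the twice-weekly ratings in the protocol's schedule required a repeated-measures model. The documents do not say when the final rating fell by arm. Final minus baseline is a natural reading of a change outcome. Some earlier SAP text and the forest predictor lists were not available, so absence from the plan cannot be shown.
- A reader might take the HAMAT_Delta sign change as hidden benefit. The visible text does not say which arm is coded 1, and both intervals span zero.

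**Conclusion.** The point holds for the printed linear models: their arm coefficients are conditional on other post-randomisation outcomes and should not be read as treatment effects on each outcome. This follows from the formulas and does not depend on the material that could not be seen.

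The numerical consequence in these data is small to moderate. The shifts are +2.18 for HAMAT_Delta (with a change of sign), +1.27 for LOS, -0.45 for MADRA_Delta and +0.05 for PSQI_Delta. Arm-alone p values run from 0.12 to 0.72, so the SAP's statement of non-significance is not overturned. What changes is the set of estimates and intervals that a later trial would carry forward.

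The reconstruction assumes that all five models were fitted to the same 30 patients, which the agreement in the working supports. The arm-alone figures are not baseline-adjusted, because the printed output has no baseline scores.

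**What to change.** Estimate the arm effect on each scale without LOS or the other change scores, adjusting only for that scale's own baseline. Compare LOS between arms without the change scores. Report each estimate with its 95% CI, state which arm is coded 1, and rest the per-outcome conclusion on these results. Keep the arm-as-response F as the joint test, described as such. If the existing models stay in the report, label them as exploratory associations among outcomes.

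The cost is analysis time and some precision: the MADRS standard error goes from 2.79 as printed to 3.69 with arm alone. Baseline adjustment should recover part of this. Assume equal baseline and final variances and a baseline-final correlation ρ of 0.3 to 0.7. The residual variance relative to a change score is then (1 + ρ)/2, or 0.65 to 0.85, and the MADRS half-width falls from about 7.6 to between 6.1 and 7.0.

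A mixed model of the twice-weekly ratings is at most an optional post hoc sensitivity analysis. It would assume that ratings after discharge are missing at random, which is doubtful if discharge depends on response.
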